[Interim Analyses]: To avoid performing a study with larger-than-necessary enrollment for Part I of our study, a formal interim analysis for the composite imaging score will be performed at approximately 20 CHD subjects for each of the contrast group (50% of the target number for the primary analysis). Alpha-spending for the interim analyses and the primary analysis will be 0.025 and 0.025 (both two-sided), respectively. The overall alpha for the composite image quality score will be preserved at the two-sided 0.05 significance level. The interim analysis of the composite image quality score will be conducted by an independent statistician under the charter of the DMC.

The interim effect of Feraheme compared to the Ablavar of ventilator-gated MUSIC-MRI based on the average composite score from two image readers will be tested with a two group t-test with an appropriate transformation if needed. Non-parametric Wilcoxon rank sum test will be considered if the data are not normally distributed based on the Shapiro-Wilk and Shapiro-Francia tests and transformation is not feasible.

18.4.2 Part II – Difference in the composite image quality score between ventilator-gated and self-gated MUSIC-MRI

The primary efficacy endpoint for Part II is the composite image quality score defined in 18.4.1. Data will be tested for normality using the Shapiro-Wilk and Shapiro-Francia tests. The composite subjective image quality score will be compared between ventilator-gated MUSIC-MRI and the self-gated MUSIC-MRI using a paired t-test with appropriate transformation if needed. If the data are not normally distributed and transformation is not possible, a Wilcoxon-sign-rank test will be considered. The null hypothesis is that the mean difference in the image quality scores of the self-gated images is smaller than or equal to the mean from ventilator-gated images with the non-inferiority margin of -1.75 (self-ventilator ≤ -1.75). The alternative hypothesis is that the mean difference in image quality score of self-gated images from the ventilator-gated images is greater than the non-inferiority margin of -1.75 (self-ventilator > -1.75) (see the detail of choosing the margin in section 18.7.2.).

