18.7 Sample Size and Power Estimate for the Primary Efficacy Endpoints

18.7.1 Part I – Difference in the composite image quality score between Feraheme and Ablavar

Sample size and power estimates are based on data from an internal pilot analysis. Based on the average composite image quality scores of two independent readers, the mean image quality score was 25.62 with a standard deviation of 1.82 for the Feraheme-enhanced, ventilator-gated MUSIC-MRI group. The difference in the image quality scores between two readers was a mean of -1.96 with a standard deviation of 2.72. We expect the agreement between two independent readings will improve with consensus reading in cases with largely different image quality scores (4 or more absolute difference in the score).

Based on the above preliminary analyses, for the interim analysis, a sample size of 20 in each contrast agent group will achieve a power of 62% to detect a difference of 1.75 (7% reduction) in the composite image quality scores between the Ablavar group and the Feraheme group with an estimated standard deviation of 2.10 in each group and a significance level of 2.5%.

In the primary analysis, a sample size of 36 subjects will achieve a power of 90% to detect a difference of 1.75 (7% reduction) in composite image quality scores between the Ablavar group and the Feraheme group with an estimated standard deviation of 2.10 in each arm and a significance level of 2.5%. Taking into consideration missing data due to unusable image quality or incomplete studies, we plan to enroll 40 CHD subjects in each group (N=80).

18.7.2 Part II – Difference in the composite image quality score between ventilator-gated and self-gated MUSIC-MRI

The quality of self-gated images are expected to be of at least equal quality to ventilator-gated images with a larger standard deviation due to variation in the methods of respiratory motion gating. We choose the non-inferior margin (87) to ensure that the upper bound of the 95% confidence interval (CI) for the difference between ventilator-gated and self-gated (ventilator – self-gated) is less than 1.75. We expect the mean of the composite image quality score for ventilator-gated images to be approximately 25.62, which is the expected upper limit of the self-gated image quality

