score. The margin of 1.75 was derived using an expected mean of 24.75 for the self-gated image (~4% reduction in image quality score compared to that achieved with the ventilator-gated method). The non-inferiority comparison will be a one-sided test at a 0.025 level of statistical significance and a -1.75 margin. A sample size of 36 will achieve a statistical power of greater than 90% to detect non-inferiority between ventilator-gated and self-gated MUSIC-MRI using a one-sided t-test with a non-inferiority margin of -1.75 and a true difference of zero with a standard deviation of 3.0 and a significance level of 2.5%. Taking into account missing data due to unusable image quality or incomplete studies, we plan to enroll 40 CHD subjects.

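### The Part II non-inferiority null concerns the mean score difference, but the optional signed-rank fallback tests a different quantity and is too lenient if self-gating fails in a minority of children

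*Combined protocol and SAP*

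**What the plan says.** Section 18.4.2 writes the Part II primary hypotheses in terms of means: "The null hypothesis is that the mean difference in the image quality scores of the self-gated images is smaller than or equal to" the ventilator-gated mean with a margin of -1.75, spelled out as self minus ventilator ≤ -1.75. Rejection is at p ≤ 0.025.

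The scores are compared "using a paired t-test with appropriate transformation if needed". Before that, "Data will be tested for normality using the Shapiro-Wilk and Shapiro-Francia tests"; no significance level is given, and the section does not say whether the tests apply to the scores or to the paired differences. The last step is: "If the data are not normally distributed and transformation is not possible, a Wilcoxon-sign-rank test will be considered". For that step the section does not restate the hypothesis, require symmetric differences, or say how the margin enters.

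Section 18.7.2 is framed in means throughout. It derives the margin from expected means of 25.62 and 24.75 and bases power on a t-test with "a true difference of zero with a standard deviation of 3.0". It confirms that "The non-inferiority comparison will be a one-sided test at a 0.025 level of statistical significance and a -1.75 margin". It also describes the margin through a confidence interval: the upper 95% limit for ventilator minus self-gated should lie below 1.75.

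**The concern.** The signed-rank test applied to difference + 1.75 has as its null that the differences are symmetric about -1.75. Under asymmetry it responds to the pseudo-median. A paragraph that defines the null as a mean therefore offers, as a last resort, a test of another quantity, and offers it when the data look non-normal.

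The direction matters. On a 7-28 scale with an expected ventilator-gated mean of 25.62, the average room to gain is 28 - 25.62 = 2.38 points and the average room to lose is 25.62 - 7 = 18.62 points. Section 18.7.2 expects self-gated scores "with a larger standard deviation due to variation in the methods of respiratory motion" gating. If that extra spread comes from a subset of children in whom self-gating fails, most differences sit near zero and a few are large losses. Ranks discount the size of those losses and the mean does not. The test can then support non-inferiority although the mean loss has reached the margin. This bears on the primary Part II claim, for a technique meant eventually for children scanned without sedation or anesthesia.

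**Working it through.** **Inputs from the plan.** Margin -1.75, one-sided 0.025, 36 evaluable children, SD of differences 3.0, true difference 0 (18.7.2). Score range 7-28 (18.3). Ventilator-gated mean 25.62, SD 1.82; between-reader difference SD 2.72 (18.7.1).

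**Step 1: reproduce the stated power.** Noncentrality = 1.75 / (3.0/√36) = 3.5 on 35 df. Exact paired t power is 92.5%, which agrees with the plan's figure of more than 90%.

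**Step 2: when the two targets agree.** With the true mean at -1.75, normal differences and SD 3.0, false non-inferiority is 2.8% for the paired t-test and 2.7% for the shifted signed-rank test. With symmetric heavy-tailed differences (t on 4 df) the signed-rank test gives 2.5%. Non-normality alone does no harm; asymmetry does.

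**Step 3: scatter in unaffected children.** The documents give no paired self-gated data, so this is assumed. A low value is SD 1.0-1.5. A higher value comes from the reader data if reader errors are independent: 2.72/√2 = 1.92 per reader, 1.92/√2 = 1.36 for the two-reader average, and 1.36 × √2 = 1.92 for the difference between two scans, so about 1.9. Consensus reading or within-child correlation would lower it.

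**Step 4: left-skewed differences on the bounded scale.** Ventilator score ~ N(25.62, 1.82), rounded to 0.5 and capped at 28. Self-gated score = ventilator score + noise in unaffected children, and ventilator score - L + noise in the failing share, rounded and clipped to 7-28. L is set so that the true mean difference is -1.75 (null true). n = 36, one-sided 0.025, test on difference + 1.75, Shapiro-Wilk at 0.05 on the differences (assumed).

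| Failing share | L (points) | SD, unaffected | SD of differences | Fallback | Paired t |
|---|---|---|---|---|---|
| 25% | about 6.7 | 1.0-1.5 | 3.1 | 11-16% | 4-5% |
| 30% | about 5.6 | 1.0-1.5 | 2.8 | 6-8% | 4% |
| 25% | calibrated | 1.9 | 3.2 | 8% | 3.6% |
| 30% | 5.4 | 1.9 | 2.94 | 5.5% | 3.4% |
| 36% | calibrated | 1.9 | 2.7 | 3.5% | 3.1% |

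The fallback column is the signed-rank rate in the first two rows and, in the last three, the rate of the rule that uses signed-rank only after Shapiro-Wilk rejects. Shapiro-Wilk rejects in over 98% of trials in the first row and 58% in the fourth. A repeat run of the 25% and 30% rows agreed within simulation error. With 3,000 trials the standard error at 5.5% is √(0.055 × 0.945/3000) = 0.4 points.

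**Step 5: rarer, larger failures at the planned SD.** In a mixture with a share p losing an extra X points, SD² = s² + p(1 - p)X². For p = 0.20, X = 6, s = 1.8: 3.24 + 0.16 × 36 = 9.0, SD 3.0. For p = 0.10, X = 9, s = 1.3: 1.69 + 0.09 × 81 = 8.98, SD 3.0. On the bounded scale the signed-rank rates are 10% and 49%. Across five such mixtures (10-20% failing, 6-9 extra points) they run from 10% to 52%; the two near 50% need s of 1.0-1.3.

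**Step 6: alternatives that keep the mean.** In those five bounded cases the paired t-test gives 4.1-7.2% and a studentised bootstrap on the mean 1.7-3.5%.

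**The case against.** Several points against this stand.

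- **The fallback is optional and last in line.** It is only to be considered, and only after transformation has failed. The rates above are conditional on reaching and choosing it. A non-linear transformation would not repair the mismatch, however, because it also leaves the raw-point scale of the margin.
- **The failure pattern is assumed.** Section 18.7.2 predicts a larger SD, not skew, and expects self-gated images to be at least as good. Section 18 limits the primary analysis to usable scans, so the worst failures may drop out and shorten the left tail.
- **The plan already holds a mean-compatible criterion.** The confidence-interval statement in 18.7.2 is the mirror image of the fix. It sits in the sample-size section and does not remove the fallback from 18.4.2.
- **The study is labelled exploratory.** This lowers the stakes but does not align the test with the null.

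A reader might infer that false claims in the range 24-67% are to be expected. In the failure model of the table such rates arise with 15-20% failing and an SD of differences of 3.5-4.1, above the planned 3.0. At SD 3.0, rates near 50% need scatter below what the reader data suggest. A reader might also infer that the signed-rank test would be run against zero, so that it tests superiority and could almost never show non-inferiority. The hypotheses stated directly after the fallback carry the -1.75 margin, so a shifted test is the natural reading. Nor is this the only Part II conclusion: 8.2.2 and 8.2.3 list secondary non-inferiority and safety endpoints.

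**Conclusion.** The mismatch is in the text and the concern holds in a limited form. The stated null is about a mean, and the permitted fallback tests the pseudo-median. Under left skew from a minority of failures, with the SD of differences near the planned 3.0, 25-30% failing and scatter of 1.0-1.9 in unaffected children, the fallback falsely declares non-inferiority in about 5-15% of trials. The paired t-test gives 3-5%, against a nominal 2.5%. The rate rises if failures are rarer and larger, falls towards the t-test's as the failing share grows, and shows no inflation when differences are symmetric.

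The size depends on assumed failure shares and scatter and on the fallback actually being used. The documents do not support reading this as a large or certain inflation. They do support saying that 18.4.2 should not leave the primary test open to a step that answers a different question.

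**What to change.** In 18.4.2, make the rule that 18.7.2 already implies the decision rule. Conclude non-inferiority only if the lower limit of the two-sided 95% confidence interval for the mean paired difference (self minus ventilator), in untransformed composite points, exceeds -1.75, whatever the normality tests show.

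Use the paired-t interval, or a studentised bootstrap interval for the same mean if the differences are clearly skewed. Fix the skewness criterion and the bootstrap details before scores are unblinded. Both intervals target the same mean, so the choice does not change the hypothesis. The bootstrap should carry the decision under skew because the paired t-test is itself mildly liberal there. Report any signed-rank or transformed analysis as supportive only.

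The cost is plan wording, with no new patients or data. The downside is somewhat less power than a rank test when a few scans are outlying.

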18.5 Secondary Efficacy Endpoints

18.5.1 Part I – Differences in individual image quality score (per segment or structure), image sharpness values, and CNR measurements for Feraheme vs Ablavar

The secondary efficacy endpoints for Part I are the individual image quality score for each of the seven anatomical structures as defined in 18.3, the image sharpness values for the ascending aorta and the interventricular septum, and the CNR measurements for each contrast agent. Data will be tested for normality using the Shapiro-Wilk and Shapiro-Francia tests. The average image quality scores of each anatomic structure between two readers, the image sharpness values, and the CNR measurements will be compared using a parametric two group t-test with an appropriate transformation if needed. If the data are not normally distributed and transformation is not possible, a non-parametric Wilcoxon-rank-sum test will be considered. Kappa statistics will be reported between two independent scores in each secondary endpoint.

18.5.2 Part II – Differences in individual image quality score (per segment or structure), image sharpness values, and CNR measurements for ventilator-gated vs self-gated MUSIC-MRI

The secondary efficacy points for Part II are the individual subjective image quality score for each of the seven anatomical structures as defined in 18.3, the image sharpness values for the ascending aorta and the interventricular septum, and the CNR measurements for the two MRI techniques. Data will be tested for normality using the Shapiro-Wilk and Shapiro-Francia tests. The average image quality scores of each anatomic structure between two readers, the image sharpness values, and the CNR measurements will be compared using a paired t-test with the margin of non-

inferiority of 0.75 for the image quality scores. If the data are not normally distributed and transformation is not possible, a non-parametric Wilcoxon-rank-sum test will be considered. Kappa statistics will be reported between two independent scores in each secondary endpoint.

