	
The primary efficacy endpoint is the sum of diagnostic image quality scores (i.e. the composite score) from the 7 pre-identified anatomical structures. A parametric two-sided t-test will be used to compare the Feraheme® group and the Ablavar® group where both groups will use ventilator-gated MUSIC-MRI. This comparison will be a two-sided test at the 0.05 level of significance. A formal interim analysis for the image quality will be performed when 20 CHD subjects in each group have completed the image acquisition. The interim analysis will be prepared by an independent statistician and presented only to the independent DMC who will make recommendations about the ongoing conduct of the study. Two hypotheses will be used to preserve the overall type 1 error rate of 0.05 between this single interim analysis and the final analysis of the mean differences in the composite image quality scores. A two-sample t-test will be used to compare the Feraheme®-enhanced and the Ablavar®-enhanced groups for the primary analysis at the 0.025 level of significance.
 
Part II: Diagnostic efficacy study to compare self-gated MUSIC-MRI with ventilator-gated MUSIC-MRI in 40 children
 
Control = Contrast agent from Part I + ventilator-gated MUSIC-MRI
 
Test = Contrast agent from Part I + self-gated MUSIC-MRI
 
Part II will start after results from Part I are available. The superior contrast agent as determined by Part I of the study or in the case that statistical significance is not achieved in Part I, the appropriate contrast agent in consultation with the DMC will be used for Part II. The primary efficacy endpoint is the composite image quality score from the 7 pre-identified anatomical structures. A parametric two-sided paired t-test will be used to compare the ventilator-gated MUSIC-MRI and self-gated MUSIC-MRI groups. The quality of the self-gated MUSIC-MRI images is expected to be not much worse than those from ventilator-gated MUSIC-MRI images. This comparison of non-inferiority will be a one-sided test at the 0.025 level of significance with a -1.75 margin in the composite image quality score.
 
SECONDARY EFFICACY ENDPOINTS:

--	---

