11 STUDY TREATMENTS

11.1 Method of Assigning Subjects to Treatment Groups

Refer to Section 7.2 for patient group assignment in Part I of the study. For Part II of the study, all subjects will undergo the ventilator-gated MUSIC-MRI and self-gated MUSIC-MRI in one imaging session in a randomized order by flipping a coin.

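### Part II: the secondary fallback ignores the pairing, the primary allows a transformation against a raw-point margin, and sharpness and CNR have no non-inferiority margin

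*Combined protocol and SAP*

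**What the plan says.** Part II is a within-child comparison. Section 11.1 states that "all subjects will undergo the ventilator-gated MUSIC-MRI and self-gated MUSIC-MRI in one imaging session", in an order set by coin toss.

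- **Primary (18.4.2).** The composite score is compared "using a paired t-test with appropriate transformation if needed". If the data are non-normal and cannot be transformed, "a Wilcoxon-sign-rank test will be considered". The hypotheses are set at -1.75 for self-gated minus ventilator-gated. The synopsis describes the test "with a -1.75 margin in the composite image quality score", and 18.7.2 requires the "upper bound of the 95% confidence interval (CI) for the difference between ventilator-gated and self-gated" to lie below 1.75. The plan gives no conversion of the margin to a transformed scale. It does not say whether normality is checked on scores or on within-child differences, or how the margin enters the signed-rank test.
- **Secondary (18.5.2).** Along with the structure scores, "the image sharpness values, and the CNR measurements will be compared using a paired t-test". The only margin given is "inferiority of 0.75 for the image quality scores" (a line break splits the word non-inferiority). The fallback is: "If the data are not normally distributed and transformation is not possible, a non-parametric Wilcoxon-rank-sum test will be considered". The same sentence closes 18.5.1, where two separate groups of children are compared and it is correct. The error is in the second occurrence only.
- **Sharpness and CNR.** Section 8.2.2, items 2 and 3, defines these endpoints as statistical non-inferiority. No section gives a margin for either. The synopsis assigns them a two-sided t-test.

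**The concern.** Three parts of the Part II analysis do not match the design or the stated hypotheses.

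1. The rank-sum test treats the two sets of scores as coming from different children. With positive within-child correlation its reference distribution is too wide, so it rejects too rarely. Section 18.5.2 also does not say that the 0.75 margin is built into it, and without the shift it tests equality.
2. A nonlinear transformation has no single equivalent of a 1.75-point loss. A transformed paired t-test would therefore address a different margin from the one in the hypotheses, and the choice would be made after the data are seen.
3. A non-inferiority endpoint without a margin has no decision rule of its own.

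Item 2 concerns the primary endpoint; items 1 and 3 concern secondary endpoints.

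**Working it through.** **Step 1. The plan's own power figure.** Inputs from 18.7.2: n = 36, margin 1.75, true difference 0, SD 3.0, one-sided 0.025. Noncentrality = 1.75 / (3.0/√36) = 3.5 on 35 df, giving power 92.5%. This agrees with the stated value of more than 90%. An unpaired reading (36 per group, SD 3.0) gives 69.7%, so only the paired analysis reproduces the plan.

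**Step 2. Why rank-sum is conservative here.** With equal SDs σ and correlation r, the difference in means has variance 2σ²(1-r)/n, while an independent-groups test assumes 2σ²/n. The effective critical value is about 1.96/√(1-r). At r = 0.5 this is 1.96/0.707 = 2.77, an upper tail of about 0.28%. Simulation on normal scores gave 0.30%.

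**Step 3. Size on the actual scale.** Pilot figures (18.7.1): composite mean 25.62, SD 1.82. Mean per structure = 25.62/7 = 3.66. With equal SDs and between-structure correlation ρ, the SD per structure = 1.82/√(7+42ρ): 0.69 at ρ = 0, 0.60 at 0.05, 0.41 at 0.3. Scores were simulated as half-points on 1-4 (average of two readers), with n = 36, one-sided 0.025 and both tests shifted by 0.75. The within-child correlations of 0.3-0.7 are assumptions, because the plan gives none.

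- Error at the margin: rank-sum 0.05-1.5%, signed-rank 2.1-3.0%.
- The plan's expectation is equal quality or, in deriving the margin, 24.75 against 25.62. Spread evenly, that is 0.87/7 = 0.12 per structure. At a loss of 0 to 0.125 both tests have 99.9-100% power.
- At 0.25 (= 1.75/7): 98.6-100% rank-sum, 99.2-100% signed-rank.
- At an assumed loss of 0.4, power (rank-sum / signed-rank, %):

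| Latent SD | r = 0.3 | r = 0.5 | r = 0.7 |
|---|---|---|---|
| 0.41 | 96.7 / 98.5 | 97.8 / 99.6 | 99.3 / 100 |
| 0.60 | 81.7 / 89.3 | 85.3 / 95.6 | 88.7 / 99.3 |
| 0.69 | 77.9 / 85.3 | 79.8 / 92.4 | 83.5 / 97.8 |

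Shapiro-Wilk rejected normality of the differences in 69-100% of these trials, so the first condition for the fallback would often be met.

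**Step 4. Transformation against -1.75.** The plan names no transformation, so these are illustrations. A log margin matched at 25.62 is ln(23.87/25.62) = -0.071. It permits a raw loss of 1.84 points from 27 but 1.37 from 20. With a reflected log, ln(29 - score), a margin matched at 25.62 permits 1.04 points from 27 and 4.66 from 20.

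Error was simulated at a true raw loss of 1.75 (n = 36; ventilator-gated SD 1.82; self-gated SD 1.82-3.0; r 0.3-0.5), transforming only when Shapiro-Wilk rejects on the differences. That happened in 8-10% of trials.

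| Analysis | Error |
|---|---|
| Raw paired t | 2.4-2.9% |
| Log | 2.3-2.8% |
| Square | 2.4-3.1% |
| Reflected log | 2.2-3.5% |

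**Step 5. Sharpness and CNR.** No arithmetic is possible, since there is neither a margin nor an SD. Section 8.2.2 asks for non-inferiority, 18.5.2 supplies a margin for image quality scores only, and the synopsis names a two-sided difference test.

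**The case against.** The strongest reply is that little is lost in practice. The fallback is only to be considered, and only if transformation also fails. The rank-sum error is conservative and confined to secondary endpoints. The primary hypotheses and confidence-interval criterion are plainly in raw points. The study calls itself exploratory. Most of this stands, and it limits the size of the point. It does not remove the contradiction between 18.4.2 and 18.5.2, or supply the missing margins.

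A reader might infer four stronger things that the documents do not support.

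- *A serious loss of power.* On normal scores (SD 0.6, loss 0.4, r = 0.5) the contrast is 71% against 91%, but the fallback applies only when normality is rejected. A loss of 0.4 in all seven structures is 7 × 0.4 = 2.8 composite points, beyond the primary margin. Only an isolated large loss in one structure makes the gap relevant.
- *An unpaired test for sharpness and CNR in the synopsis.* The sentence compares two *groups*, but it follows on, by way of *Similarly*, from a paired t-test. The synopsis also calls the two paired techniques groups in its primary analysis. An unpaired intention is not established.
- *A doubled primary error rate.* A figure of 5.2% can be produced, but it needs a transformation the plan does not name, a margin conversion it does not give, and a normality check on scores rather than on differences.
- *Non-significance read as non-inferiority.* No section says so. A result significantly favouring self-gating would also support non-inferiority without a margin.

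**Conclusion.** The point holds as a specification fault of modest practical size that should be corrected before any Part II data are seen.

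- The rank-sum fallback in 18.5.2 is wrong for the design and inconsistent with 18.4.2. If margin-shifted, it is conservative under positive correlation, with negligible power loss at the losses the plan expects. If unshifted, it does not test non-inferiority.
- A transformed primary test would not test the stated -1.75 margin, although the likely effect on the error rate is small.
- Sharpness and CNR cannot be tested for non-inferiority as such, and the two-sided test in the synopsis is not a non-inferiority test.

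The contradiction and the missing margins rest on the text alone. The sizes rest on assumed correlations, equal structure SDs derived from the pilot composite, and illustrative transformations. The plan's stated primary power is sound.

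**What to change.** - **18.5.2:** as the fallback for structure scores, name the signed-rank test on within-child differences (self-gated minus ventilator-gated) shifted by the 0.75 margin.
- **18.4.2:** delete the allowance for transformation. Test untransformed within-child differences and conclude non-inferiority if the lower limit of the paired 95% confidence interval exceeds -1.75. Check normality on those differences. State that the signed-rank fallback is shifted by 1.75.
- **8.2.2, items 2 and 3:** either prespecify justified margins for sharpness and CNR before any Part II data are seen, or drop the non-inferiority wording and report paired mean differences with 95% confidence intervals.
- **Synopsis:** make clear that the sharpness and CNR comparison is paired.

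**Cost.** No new data, no change in sample size, and primary power unchanged at 92.5% with 36 children. Sharpness and CNR may become estimates only. The signed-rank test addresses the pseudomedian rather than the mean. Its simulated error is 2.4-3.1% as the primary fallback and 2.1-3.0% for structure scores, rising to 3.9% if the self-gated latent SD is 0.9 (paired t up to 3.2%).
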